- We believe that this study will generate an estimate of the effect that can be used to inform the development of randomized controlled studies (RCTs).
 - This study will also generate RCTs examining the use of the Oculus VR as a form of stroke rehabilitation that is scalable to the participant's home setting.
 - There are few studies that have examined the role of caregiver engagement on the success of remote stroke rehabilitation.
- The caregiver will be encouraged to use Caregiver Cues (Appendix D) as this will help the caregiver to engage with the participant using encouragement or positive cues to the stroke participants to support them during the session.
- The therapist or RA (who will be trained by the therapist) who is conducting the session will use the Therapist Guided Cues (Appendix E) to guide the stroke participant with problem solving and planning for performing home exercises that will be provided to the participant at the first session.
- The data we obtain from caregivers and stroke survivors (dyads) will inform future studies that examine ways to best support the dyads to improve stroke rehabilitation outcomes and reduce stress in the caregivers. (See Appendix F)

Statistical Analysis

- To address S.A.1., feasibility, usability, and acceptability of the Oculus VR headsets for upper extremity and cognitive therapies will be analyzed as follows: Feasibility: Assessed from the number sessions attended and time spent using the Oculus VR. The minimum number of sessions expected for a user are 2 per week (8 sessions) and the minimum time spent playing Job Simulator is 1 hour per week (4 hours) through the end of the study. Descriptive statistics of the participation rates and measures including frequencies, median and interquartile ranges for sessions attended and time spent using the game. Usability: Descriptive statistics for demographic and clinical data and participant scores on the SUS and PQ will be calculated. (See Appendix G and H) We will refrain from using inferential statistics since this is a pilot study and hypothesis testing is not the objective. Acceptability: Descriptive statistics for scores on the SSQ will be calculated at baseline and after each session (See Appendix I). We will examine the trend of symptoms for each participant.)

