Number of sessions attended; Duration (minutes) of session	Session 1 – Last Session		

Table 1

Potential Problems and Alternative Approaches

- If the participant cannot complete the study, then we will offer home exercises selected by the therapist from Appendix N and they will exit the study.
- Stroke survivors will be encouraged to take a brief break every 20 minutes due to potential for visual fatigue. If the participant develops simulator sickness (e.g., nausea, dizziness, etc.) or wishes to stop the session for any reason, we will immediately stop the session and allow the participant to rest until the symptoms subside.
 - If the participant's symptoms do not resolve immediately, then we will take the patient's blood pressure, pulse, and/ or temperature as appropriate.
 - We will call 911 should the participant require immediate assistance. If the participant does not require immediate care, we will encourage the participant to be evaluated at an urgent care and/ or their doctor's office.

- All adverse events will be monitored, documented, and reported to the ethics committees. Progress addressing adverse events will be recorded until their resolution.

Data Management

- We will record the Oculus gaming sessions using the camera located in the living room for the therapists to review after the session to evaluate the participants' progress.
- Informed consent documents and de-identified, demographic and participant satisfaction surveys will be stored electronically via REDCap,™ following UTHealth security procedures. Qualitative interview data will be digitally recorded; these raw audio files will be stored in a secure folder of the PI's UTHealth, OneDrive. Transcribed, de-identified interview data will be managed and analyzed via Atlas.ti.™

Collaboration and Interaction Plan

- The proposed interdisciplinary project brings together highly experienced investigators in diverse areas of research and clinical practices.
- The project is built from developing new collaborations between investigators across institutions including the University of Texas Health Science Center at Houston (UTHealth).
- The team will be led by

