Appendix E

Therapeutic Guided Cues Protocol^{12,13} for the Stroke Survivor Participants to be Used by the Research Assistant .

During the session:

Problem solving:

- What will you gain by doing exercises at today's session?
- (Reinforce with the patient) Flexible coping strategies include:
 - define the problem and goal
 - generate multiple solutions
 - select a solution
 - implement and evaluate

Decision making:

- What will you do if you start to feel dizzy or not well during today's session?

Resource utilization:

- How will you seek assistance from your caregiver today during the session?
- You can ask me to assist you during the session. How will you signal to me that you want to stop?

Partnership with rehabilitation therapist/ RA:

- Do you understand what I am asking you to do?
- Would you like to practice the arm/ hand movements (or using the hand controller) with me before starting the session?

Planning and taking action:

- How will you use the hand controller?
- How will you put the headset on? Who will assist you?
- How many times this week will you come to the AIP apartment for your rehabilitation session?

For arm/ hand exercises at home:

Problem solving:

- What will you gain by doing arm/ hand exercises at home?

Decision making & Planning and taking action:

- Where/ when/ what/ how will you do your arm/ hand exercises?
- How will you know if you are doing your arm/ hand exercises correctly?
- How will you know when to stop doing your hand/ arm exercises?

Resource utilization:

- Can a friend or family member assist you with your arm/ hand exercises?
- Do you have a non-slippery surface at home where you can do your exercises?
- Do you have slip-resistant shoes?

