Appendix M
Therapy Follow Up Checklist

**Please answer the following questions regarding therapy visits
that have been received since the last study visit**

Occupational Therapy	YES/NO	# of sessions	Session Length
Therapy addressed:	 Home exercise program  Self-care (dressing, toileting, etc)  Household tasks (cooking, cleaning, etc)  Return to worktasks  Coordination  Community tasks (shopping, using public transportation, etc)  Cognition (memory, multi-tasking, attention, etc)	 Transfers  Casting/splinting  Vision  Sitting/standing balance  Arm/hand exercises - Number of repetitions: _____	
Physical Therapy	YES/NO	# of sessions	Session Length
Therapy addressed:	 Walking  Running  Vestibular exercises  Leg exercises - Number of repetitions: _____	 Rolling in bed  Standing balance  Transfers  Casting/bracing - Number of repetitions: _____	 Sitting balance  Home exercise program  Getting in/out of bed  Core exercises - Number of repetitions: _____
Speech Therapy	YES/NO	# of sessions	Session Length
Therapy addressed:	 Cognition (memory, multi-tasking, attention, etc)  Communication (speaking and/or understanding)  Swallowing		

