Appendix N

Home Exercises that the Rehabilitation Therapist will Select for the Stroke Survivor

HEP2GO Home Exercise Program
Created by [name], OTR Apr 15th, 2022

View videos at www.HEP.video

Total 11

SCAPULAR RETRACTIONS
Move your shoulder blades back and down.
Hold, relax and repeat.

[figure not shown]
Repeat 10 Times
Hold 5 Seconds
Complete 2 Sets
Perform 4 Times a Week

AROM SHOULDER ABDUCTION
With your affected arm starting at your side with your thumb pointed upward, raise up your arm to the side.

Repeat 10 Times
Hold 5 Seconds
Complete 2 Sets
Perform 4 Times a Week

Video # VVNFC7TNL

AROM FLEXION
While sitting or standing with your arm at your side, slowly raise it up and forward towards overhead.

Repeat 10 Times
Hold 5 Seconds
Complete 2 Sets
Perform 4 Times a Week

Video # VVBNSZXGV

Total 13

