 Arrange sessions schedules with Dyads for the length of the study (2 sessions/week each being an hour minimum in length). Reserve smart room for duration of study.	

 _ Complete the Pre-Intervention Questionnaire (Secondary Outcome; Appendix R) 	

 _ Have the stroke survivor complete the Simulator Sickness Questionnaire (SSQ) at the beginning and end of the first 1-hour session (Primary Outcome; Appendix I) 	
2nd Session (Week 1)	Initial & Date completed

 _ Research Assistant complete the Therapy Follow Up Checklist with Subject before the start of the session. (Secondary Outcome; Appendix M) 	

 _ Have the stroke survivor complete the Simulator Sickness Questionnaire (SSQ) at the beginning and end of the second 1-hour session (Primary Outcome; Appendix I) 	
3rd Session (Week 1)	Initial & Date completed

 Research Assistant complete the Therapy Follow Up Checklist with Subject before the start of the session. (Secondary Outcome; Appendix M) 	

 Have the stroke survivor complete the Simulator Sickness Questionnaire (SSQ) at the beginning and end of the third 1-hour session (Primary Outcome; Appendix I) 	
4th Session (Week 2)	Initial & Date completed

 Research Assistant complete the Therapy Follow Up Checklist with Subject before the start of the session. (Secondary Outcome; Appendix M) 	

 Have the stroke survivor complete the Simulator Sickness Questionnaire (SSQ) at the beginning and end of the fourth 1-hour session (Primary Outcome; Appendix I) 	
5th Session (Week 2)	Initial & Date completed

 Research Assistant complete the Therapy Follow Up Checklist with Subject before the start of the session. (Secondary Outcome; Appendix M) 	

 Have the stroke survivor complete the Simulator Sickness Questionnaire (SSQ) at the beginning and end of the fifth 1-hour session (Primary Outcome; Appendix I) 	
6th Session (Week 2)	Initial & Date completed

 Research Assistant complete the Therapy Follow Up Checklist with Subject before the start of the session. (Secondary Outcome; Appendix M) 	

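### The plan promises to monitor and document all adverse events, but no form or scheduled question asks about new events outside the sessions

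*Combined protocol and SAP*

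**What the plan says.** Potential Problems and Alternative Approaches makes two commitments. The first concerns scope: "All adverse events will be monitored, documented, and reported to the ethics committees". The second concerns follow-up: "Progress addressing adverse events will be recorded until their resolution". The concrete steps in that section deal with symptoms that arise during a session, when "we will immediately stop the session and allow the participant to rest until the symptoms subside". The section does not say how, when or on what form events outside a session are to be found.

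Appendix Q sets out the visits. At each of the 12 sessions the SSQ is given twice; for session 2, for example: "Have the stroke survivor complete the Simulator Sickness Questionnaire (SSQ) at the beginning and end of the second 1-hour session". Before sessions 2 to 12 the research assistant completes the Appendix M checklist, which opens "Please answer the following questions regarding therapy visits" and covers occupational, physical and speech therapy since the last study visit.

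The Intervention section has the therapist or research assistant guide participants in planning and "performing home exercises that will be provided to the participant at the first session". The exercises printed in Appendix N carry the instruction "Perform 4 Times a Week", and the home-exercise cues in Appendix E include "Do you have slip-resistant shoes".

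**The concern.** The commitment covers every adverse event, but the scheduled data collection does not reach that far. Staff who follow the visit checklists exactly as printed would never ask whether a participant had fallen, been hurt, had a seizure or seen a doctor since the last visit.

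The plan itself treats some of these as relevant. The Appendix R questionnaire takes a history of falls and of seizures or blackouts at entry, and no later form returns to them. Appendix E asks about footwear and a non-slip surface for exercise at home. Much of the sample is likely to have mild to moderate cognitive impairment, given the eligibility criteria, which makes reliance on volunteered reports weaker than usual.

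What is at stake is how a low event count will be read. The study is meant to supply preliminary data on acceptability for at-home use and to inform a randomised trial. A small number of events from questions that were never asked could be taken as evidence of safety.

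**Working it through.** The documents state no adverse-event rate, precision target or power calculation, so there is no figure to reproduce. The check sets each collection point beside the commitment.

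| Collection point | When | What it captures | What it misses |
|---|---|---|---|
| SSQ (Appendix I) | Start and end of each session | 16 simulator-type symptoms; the printed form states no recall period | Falls, injury, arm or shoulder pain, seizures, medical visits |
| Therapy Follow Up Checklist (Appendix M) | Before sessions 2 to 12 | Therapy received since the last study visit | Any health event |
| Post-intervention interview (Appendix S) | Last session | A probe on symptoms or headset features that would deter re-use | Events unrelated to re-using the headset |
| Visit checklists (Appendix Q) | Every visit | Completion of the listed instruments | No adverse-event line |
| Call after session 12 (Appendix Q) | Only if post-intervention items are missing | Those missing items | New events |

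Adverse events do not appear in Table 1, in the Appendix A list of instruments or in the Statistical Analysis section.

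**By time window**

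- *Between sessions.* A simulator-type symptom still present at the next visit can show on the pre-session SSQ. A symptom that has cleared may not. A fall or a medical visit has no item at all. The Statistical Analysis section names SSQ summaries at baseline and after each session, so pre-session scores from session 2 onward are collected without being named in the analysis.
- *During home exercise.* The exercises are given from session 1. There is no exercise log and no event question attached to them.
- *After session 12.* No contact is scheduled except to complete missing items.
- *After early exit.* A participant who cannot complete is offered home exercises and leaves. No later contact and no event question at exit is described.

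**Why the capture rate matters: an illustration only**

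Input from the plan: n = 20 stroke survivors. Assumed, and not in the documents: the true risk p that a participant has an event of interest, and the fraction c of affected participants whose event reaches the record.

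Chance of recording at least one affected participant = 1 − (1 − p·c)^20.

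One-sided 95% upper bound on the true risk when none is recorded = (1 − 0.05^(1/20)) / c.

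| c | p = 5% | p = 10% | p = 20% | Upper bound if none recorded |
|---|---|---|---|---|
| 1 | 64.2% | 87.8% | 98.8% | 13.9% |
| 0.75 | 53.4% | 79.0% | 96.1% | 18.5% |
| 0.5 | 39.7% | 64.2% | 87.8% | 27.8% |
| 0.25 | 22.2% | 39.7% | 64.2% | 55.6% |

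For example, at p = 10% and c = 0.5: 1 − (1 − 0.05)^20 = 64.2%. With no recorded events and full capture, 20 participants exclude a risk above 13.9%. At half capture the same result excludes only a risk above 27.8%. The table shows sensitivity to c; it does not estimate c.

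**The case against.** The strongest reply is that this is a single-arm feasibility pilot of 20 dyads with mainly descriptive aims, and that no planned analysis uses an adverse-event count. Staff see participants up to three times a week. Every VR session takes place in the study apartment with staff and a camera, and with the SSQ before and after. Appendix D also encourages the caregiver to write down issues for the therapist. On this view, spontaneous reports would reach the record, and participant instructions may sit in consent pages that were not available here.

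Much of that stands. It means that exposure to VR itself is well observed and that no primary conclusion turns on this gap. It does not supply a question about falls, injury, pain, seizures or medical visits. The informal routes depend on someone choosing to mention an event, and the Appendix Q checklists, which are available, do not prompt for one.

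Four stronger readings are tempting, and the documents do not support them.

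- *That nothing at all is collected between sessions.* The pre-session SSQ can pick up persisting simulator-type symptoms, and the interview has a symptom probe.
- *That the early-exit sentence contradicts follow-up to resolution.* It says the participant leaves the study. It does not say that recording of an open event stops, and the follow-up commitment makes no exception for leavers.
- *That exposure shares measure missed events.* A reader might set 4 × 4 × 20 = 320 home-exercise occasions against 12 × 20 = 240 sessions and get 320/560 = 57%, or set 12 session hours against 4 × 7 × 24 = 672 hours and get 1.8%. Both describe exposure. The first also assumes full adherence and applies the Appendix N frequency to the session-1 exercises, although the Intervention section cites neither that appendix nor a frequency.
- *That the gap falls on unsupervised home VR use.* The stated goal is acceptability for at-home use, with caregiver participation to be studied; it is not described as unsupervised. The home exercises printed here are conventional arm exercises without a headset.

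**Conclusion.** The concern holds as a gap between a stated commitment and the procedures behind it. For events outside the sessions, other than simulator-type symptoms still present at a visit, the plan relies on volunteered reports. Such events are likely to be under-counted, by an amount that the documents do not allow anyone to estimate. The inference of under-counting rests on two assumptions: that unprompted reporting is incomplete, and that no reporting instruction in the unavailable pages fills the gap.

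The feasibility, usability and change-score analyses are not affected. The consequence is limited to the harms record and to what a low or zero count can be taken to mean when the next trial is planned. It is worth correcting because the remedy is small and uses a form already in place.

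**What to change.** 1. Add one item to Appendix M, completed before each of sessions 2 to 12: since the last visit, has there been any fall, new or continuing symptom, pain, seizure or unplanned medical visit? Record the onset and whether it followed a VR session or home exercise.
2. Ask the same item once at or shortly after session 12, and at early exit, using the video-call route that the plan already has. Add a matching line to the Appendix Q checklists.
3. State that leaving the study does not end the promised recording of an open event until it resolves. This clarifies two compatible sentences.
4. Add a descriptive summary of events by setting (VR session, home exercise, other) to the Statistical Analysis section, with the number of participants asked at each point so that the denominator is known.

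Cost: the item would be asked at most 11 times per participant, or 11 × 20 = 220 times in all, at a few minutes each. There would be one short extra contact per participant, so at most 20. The reported event count will probably be somewhat higher, and the report should say that events were actively elicited. No treatment, schedule or stopping rule changes.

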- The data will serve as preliminary data for subsequent competitive, peer-reviewed extramural grant applications that address telerehabilitation in stroke survivors within the home and the role of their caregiver.
 - Specifically, the proposed project addresses priorities outlined by institutes (e.g., National Institute of Neurological Disorders and Stroke, National Institute of Aging and National Institute of Nursing Research) within the National Institutes of Health (NIH) by investigating innovative approaches to promote health and well-being in patients and their informal caregivers living within the confines of a chronic disease. Specifically, stroke survivor acceptability data and knowledge derived from commercially available VR headset technology are needed to demonstrate:
 - The technology is acceptable for at-home use in stroke populations
 - The technology is capable of effecting improvement in upper extremity motor movement and cognition in stroke survivors.
- We will use the data from the proposed project to determine and complete the needed modifications to the home rehabilitation program using the Oculus VR headset in the post-stroke population.
- The data from this study will be used to plan an RCT to test the effectiveness of the intervention on improving upper extremity functionality and cognitive outcomes that can lead to improved independence during activities of daily living.
- We also plan to examine the role of the caregiver on home rehabilitation outcomes and the impact of caregiver participation during home rehabilitation sessions on stroke survivor-informal caregiver dyads and on caregiver burden.
- We anticipate submitting grant applications to the NIH and other appropriate foundations within 3 months from the time this project is completed.

References

Appendix A
Description of Instruments

Variables	Specific Aims	Stroke Participants	Informal Caregiver	Data Collection Procedures
		Measures/Descriptions	Measures/Descriptions	
Pre-Intervention Questionnaire (Appendix R; Secondary Outcome)		Demographic data will be collected via survey (e.g., age, sex, race, education, health history, prior technology use, etc.)	Demographic data will be collected via survey (age, sex, race, education)	Baseline (RedCap), The PI, therapist, and/ or RA will review the data with the participants)
Feasibility (Primary Outcome)	SA1	Number of sessions attended; Duration (minutes) of session	N/A	Continuous – PI, therapist, and/ or RA will maintain log
Usability (Appendix G; Primary Outcome)	SA1	The System Usability Scale (SUS) ¹ measures the impact, perceived usefulness and ease of use, and user control of the technology using a 5- point Likert scale (1= strongly agree to 5= strongly disagree) with a score range 0-100. Higher scores (>68) indicate higher perceived usability. The SUS is a widely-used 10-item validated instrument with a Cronbach's alpha of .91. ²	N/A	Post-intervention (RedCap)

Variables	Specific Aims	Stroke Participants	Informal Caregiver	Data Collection Procedures
		Measures/Descriptions	Measures/Descriptions	
Usability (Appendix H; Primary Outcome)	SA1	The Presence Questionnaire (PQ ver.3) evaluates the user's level of presence in the VR environment on a 7-point scale with 1 being the lowest and 7 the highest level of presence. The PQ is widely-used in VR research is a validated instrument with a Cronbach's alpha of .91. ³		of 87% in detecting mild cognitive impairment ⁶ .
Acceptability (Appendix I; Primary Outcome)	SA1	The Simulator Sickness Questionnaire (SSQ) ⁴ is comprised of 16 items that capture physical symptoms commonly associated with prolonged activity in a simulator. Each symptom is ranked in order of effect on the user (none, slight, moderate, severe.). The SUS is widely-used in VR research is a validated instrument with a Cronbach's alpha ranging from .84-.94 on subdimensions. ⁵		
Cognitive Assessment (Appendix J; Primary Outcome)	SA2	The Montreal Cognitive Assessment (MOCA) is a 30-item screening tool used to detect cognitive impairment that takes 10 minutes to complete. It measures cognition measures including attention and memory. The MOCA has good evidence of internal consistency (Cronbach's alpha = .82) and test-retest reliability (r = .92) ⁶ . At a cutoff score of 26, MOCA has a sensitivity of 90% and specificity		

N/A

P
o
s
t
-
i
n
t
e
r
N/A
e
n
t
i
o
n
(
R
e
d
C
a
p
)

nuous – the participant
will be evaluated with the
SSQ by PI, therapist, or
RA before and after the
intervention

Baseline & Post-
Intervention - the PI,
therapist or RA will
conduct the cognitive
evaluation

N/A

C
o
n
t
i

Variables	Specific Aims	Stroke Participants	Informal Caregiver	Data Collection Procedures
		Measures/Descriptions	Measures/Descriptions	
Upper Limb Assessment (Appendix K; Primary Outcome)	SA2	The Fugl-Meyer Assessment-Upper Extremity ⁷ is scored on 7 domains on a 3-point scale (0 - cannot perform, 1 -performs partially, 2 - performs fully) for a total of 66 points. It is a validated instrument with a Cronbach's alpha of .88-.90. ⁸	N/A	Baseline & Post intervention – the occupational therapist and/ or RA will conduct the upper extremity assessment
Upper Limb Assessment (Fine motor) (Appendix L; Primary Outcome)	SA2	The Action Research Arm Test (ARAT) has 19 items with 4 subscales (grasp, grip, pinch, and gross movement) and arranged in order of decreasing difficulty. Scoring is recorded on a 4-point scale (0 – no movement, 1 – movement is partially performed, 2 – completed task but abnormally long amount of time, 3 – movement is normal) for a total of 57 points. It is a validated instrument Cronbach's alpha of .98. ^{9,10}	N/A	Baseline & Post intervention – the occupational therapist and/ or RA will conduct the upper extremity assessment
Caregiver Burden (Appendix F; Primary Outcome)	SA3	N/A	The Burden Scale for Family Caregivers (BSFC-s) is a 10-item questionnaire using a 4- point Likert scale (1= strongly agree to 4= strongly disagree). BSFC-s has a Cronbach's alpha of .92 and adequate evidence of convergent and discriminant validity (Giessen Symptom Complaints List-24: r = 0.68; Caregiver Strain Index: r =	

0
.7
0
;
B
e
r
l
i
n
n
v
e
n
t
o
r
y
o
f
C
a
r
e
g
i
v
e
r
s
,

B
u
r
d
e
n
w
i

th Dementia Patients: $r = 0.16$; $p < 0.001$) for

Baseline & Post- Intervention (RedCaep)

n

1

1

.

Variables	Specific Aims	Stroke Participants	Informal Caregiver	Data Collection Procedures
		Measures/Descriptions	Measures/Descriptions	
Post-Intervention Questionnaire (Appendix Secondary Outcome)	SA1& SA3 S;	A semi-structured interview will be conducted to gather information on the stroke survivors' attitudes towards the intervention. Additional questions will be asked about the caregiver-stroke survivor dyad.	A semi-structured interview will be conducted to gather information on the caregiver's attitudes towards the intervention. Additional questions will be asked about the caregiver-stroke survivor dyad.	Post-intervention – conducted by PI, therapist, and/or RA

